		5.2.1 Consent Process		

An individual accessing the REDcap screening survey (for study qualification) is first presented with an electronic version of the Screening Consent form. A check-box option to proceed to the survey, indicating implied consent for the screening procedure, is required in REDCap before advancing to the survey. Screening consent is not associated with a particular location, although the Screening Consent form indicates that survey questions may be sensitive in nature

(therefore it is at the discretion of an individual to proceed if accessing the electronic survey in a public setting).

After completing the electronic screening process, qualifying participants will schedule an inperson Informed Research Consent appointment with an IRB-approved study team member who is designated as "involved in consent" in the CATS IRB system. Participants may review the consent form in advance, and will be encouraged to consult with family, friends, their PCP, or anyone else that they may wish to consult before deciding whether to participate.

Informed Research Consent may be completed in the participant's personal residence, in a private area of a participant's community living facility, or in the laboratory space of the PI on the PSU-UP campus. A qualified study team member will inform the subject of all study requirements before the subject decides whether or not to participate. Participants will be able to review the consent document and address questions or concerns prior to completing the form (either hard-copy or electronically in the REDCap system). Study coordinators, the Principal Investigator, and other study staff will engage in the ongoing process of informing subjects about study conditions and other information that will inform their decision about whether or not to continue participating. Participants will be offered a copy (electronic or physical) of the Informed Research Consent for their records.

The study team member will also sign to indicate having conducted consent with a given subject/ID.

In the event that a study volunteer elects to take more time to consider participation before choosing to proceed with the Informed Research Consent at their appointment, study staff will attempt to maintain contact with the study volunteer until such time as the volunteer decides to either schedule another appointment for Informed Research Consent completion or to withdraw.

5.2.2 Coercion or Undue Influence during Consent

It is stated in the Screening and Informed Research Consent Forms that participation in this research is completely voluntary, that not being involved does not have any negative consequences, and that participants may withdraw from the study or their consent at any time without repercussions to them.

Waiver of Written Documentation of Consent 5.3

5.3.1 	Indicate which of the following conditions applies to this research: The research presents no more that minimal risk of harm to subjects and involves no procedures for which written consent is normally required outside of the research context.
OR	
	The only record linking the subject and the research would be the consent document and the principal risk would be potential harm resulting from a breach of confidentiality. Each subject will be asked whether the subject wants documentation linking the subject with the research and the subject's wishes will govern. (Note: This condition is not applicable for FDA-regulated research . If this category is chosen, include copies of a consent form and /or parental Page 9 of 23 (IRB USE ONLY: V.02/01/2023)

permission form for participants who want written documentation linking them to the research.)

OR

If the subjects or legally authorized representatives are members of a distinct cultural group or community in which signing forms is not the norm, that the research presents no more than minimal risk of harm to subjects and provided there is an appropriate alternative mechanism for documenting that informed consent was obtained. (*Note: This condition is not applicable for FDA-regulated research.*)

For distinct cultural groups describe the alternative mechanism for documenting that informed consent was obtained:

5.3.2 Indicate what materials, if any, will be used to inform potential subjects about the research (e.g., a letter accompanying a questionnaire, verbal script, or implied consent form)

The HRP-585 Screening Consent template is used to sufficiently inform potential subjects about the research.

5.4 Consent – Other Considerations

5.4.1 Non-English-Speaking Subjects

Non-English speakers will not be enrolled in the study.

5.4.2 Cognitively Impaired Adults

5.6.2.1 Capability of Providing Consent

Subjects who are independent living and indicate both a physical and cognitive capability of self-care will be eligible to participate in the study. Participants will initially self-attest to these criteria on a screening qualification survey and will be further screened by a research team member at full consent. The enrollment population age range in this research is unlikely to present issues related to cognitive decline/MCI.

5.6.2.2 Adults Unable to Consent

Not applicable; those who cannot provide their own informed consent will not be enrolled in the study.

5.6.2.3 Assent of Adults Unable to Consent

Not applicable; those who cannot provide their own informed consent will not be enrolled in the study.

5.4.3 Subjects who are not yet adults (infants, children, teenagers)

5.6.3.1 Parental Permission

Not applicable; subjects must be 40-65 years of age.

5.6.3.2 Assent of subjects who are not yet adults

Not applicable; subjects must be 40-65 years of age.

6.0 Study Design and Procedures

6.1 Study Design

This 8-week, randomized, cross-over, at-home clinical trial of mid-life adults (men and women aged 40-65 years) consists of four segments: Baseline (week 1), active Intervention/Control (weeks 2-4), Washout (week 5), and active Intervention/Control (weeks 6-8).

6.2 Study Procedures

General overview

Participants complete Screening Consent in REDCap and, if eligible based on screening surveys, schedule their consent appointment and study dates.

Participants complete an Informed Research Consent in-person with study staff. Participation in the ~8wk study begins immediately after completion of this consent.

Throughout the entire ~8wk study:

- -Ambulatory sleep measurement (via wrist-worn actigraphy, day and night ~24hrs)
- -Twice daily self-assessment of sleep, related activities, and device usage (via REDCap sleep diaries [~1min each, totaling ~2min daily]) administered in the morning ("Morning" survey in CATS) and evening ("Bedtime" survey in CATS)
- -Weekly REDCap surveys (participants receive survey link at either/both their personal email or phone number [by text message], according to their preference; ~15min each). Participants may choose to receive email or text message reminders, or phone/voicemail reminders, to their personal accounts/devices about surveys
- -Responding to questions by staff during each study visit to determine ongoing qualification and possible study events

Overview of 4 study parts (details in below, specific sections):

- -"Baseline": Baseline data collection without sleep pad device present/in-use (week ~1) and randomization. Objective sleep monitoring for 2 nights. Blood sample (up to 40cc / up to 3 tablespoons) collected.
- -"Phase 1": Active intervention/control with either the sleep pad or an identical-looking/operated 'sham' pad present/in-use nightly (weeks ~2-4). Objective sleep monitoring for 2 nights. Blood sample (up to 40cc / up to 3 tablespoons) collected.

- -"Washout": Break from presence/use of the sleep pad device (week ~5)
- -"Phase 2": Active intervention/control with either the sleep pad or an identical-looking/operated 'sham' pad present/in-use nightly (weeks ~6-8). Objective sleep monitoring for 2 nights. Blood sample (up to 40cc / up to 3 tablespoons) collected.

All participants will complete all parts of the study (i.e. both intervention and control) but the order in which they experience these conditions will be randomized at the end of Baseline week after verifying compliance with study procedures and eligibility to continue.

All visits may take place in either a participant's personal residence or privately at the PSU-UP campus, excepting for participants whose distance from campus is too great for staff commute (i.e., more than about 20min one-way). In those cases, participants must come to the PSU-UP campus for study visits.

Specific study procedures

Polysomnography (PSG): A cluster of measures acquired by bioelectrically-sensitive sensors that include EEG (neurocortical field potentials), EOG (ocular muscle), EMG (chin), and EKG (cardiac activity). Surface (non-invasive) electrodes will be applied to specific locations on the subject's face, head, and chest using temporary adhesives that are designed for clinical use on humans. Our sleep monitoring system permits ambulatory collection via a portable amplifier worn/carried as participants go about their regular activities, with the exception of bathing.

Actigraphy: Activity-sensitive wrist-worn ambulatory device that is non-invasive. Records signals pertaining to motion activity and light exposure. An "on-wrist detection" feature permits compliance verification on devices to determine valid recordings.

Surveys:

Insomnia Severity Index (ISI) - The ISI assesses perceived severity of insomnia. The ISI has an internal consistency alpha coefficient of 0.74, and has shown convergent validity with other measures such as the Pittsburgh Sleep Quality Index (r = 0.67), the Dysfunctional Beliefs and Attitudes about Sleep (r = 0.55), and sleep diaries (range from 0.32-0.91). ^{10, 11}

PROMIS Pain Intensity and Interference (PI&I) – The PI&I assesses retrospective average weekly pain both in terms of severity and functionality. Intensity: A weekly self-report quantifying pain on a visual analog scale. Interference: A weekly self-report on a visual analog scale of whether and how much pain interfered with typical daily experiences. Responses to these exploratory surveys are expected to change (improve) as a function of sleep (improvement).¹⁴

6.2.1 Visit 1 - Informed Research Consent and Baseline Start

Informed Research Consent and study initiation (including and initial intake survey [please refer to CATS attachments "Race/Ethnicity Survey," "Socioeconomic Survey," and "Health History Survey"] and collection of payment information (consistent with PSU tax reporting requirements) will take about 1hr to complete. Upon completion:

- -Participants receive instruction regarding, and begin data collection with, ambulatory activity (actigraphy) monitor
- -Participants are equipped with abbreviated Polysomnography (PSG) monitoring equipment and recording is initiated

Above procedures after Consent take about 1 hour to complete.

-Participants may return home (if applicable) and are continuously monitored throughout the subsequent remaining day and overnight with PSG

6.2.2 Visit 2 (Baseline)

Study team members visit the participant the following morning to remove PSG.

Above procedures take about 30min 'active' engagement to complete.

6.2.3 Visit 3 (Baseline)

After at least one overnight without PSG, another participant visit occurs.

- -Actigraphy device is exchanged (for later compliance evaluation).
- -Participant is re-equipped with abbreviated PSG and recording is initiated
- -Participants return home (if applicable) and are continuously monitored throughout the subsequent remaining day and overnight with PSG

Above procedures take about 1hr 'active' engagement to complete.

6.2.4 Visit 4 (Baseline)

Study team members visit the participant the following morning to remove PSG.

-Participants whose actigraphy data evidence compliance and with at least one successful overnight PSG monitoring proceed in the study. Participants whose activity data suggest noncompliance or who experience technical failure of either actigraphy or PSG during the first study week may have the option (at researcher discretion) to repeat their first week of study activities up to this point without additional compensation.

Above procedures take about 30min 'active' engagement to complete.

6.2.5 Visit 5 (Baseline)

Participant has a fasted (~8hrs immediately preceding the appointment, no food and limited water intake) blood draw conducted by qualified Clinical Research Center (CRC; Noll Laboratory) staff.

-Participant completes weekly REDCap surveys

Above procedures take about 30min 'active' engagement to complete.

6.2.6 Visit 6 (Baseline)

Qualifying participants are randomized to an order of study conditions upon completion of this visit.

-Participant receives the Frequen-ZZZ sleep pad device or sham device (consistent with their randomization order; participant will not be informed of their assignment) and is trained on its setup/use

Above procedures take about 30min 'active' engagement to complete.

6.2.7 Visit 7 - Phase I Start: Intervention or Control

Near the end of the 3rd study week, participants have an in-person study visit to be equipped with abbreviated PSG monitoring. Overnight recording is initiated.

Above procedures take about 1 hour 'active' engagement to complete.

-Participant returns home (if applicable) and is continuously monitored throughout the subsequent remaining day and overnight with PSG

6.2.8 Visit 8 (Phase I)

Study team members visit the participant the following morning to remove PSG.

Above procedures take about 30min 'active' engagement to complete.

6.2.9 Visit 9 (Phase I)

Near the end of the 4th study week, participant is re-equipped with abbreviated PSG. Overnight recording is initiated.

Above procedures take about 1hr 'active' engagement to complete.

-Participant returns home (if applicable) and is continuously monitored throughout the subsequent remaining day and overnight with PSG

6.2.10 Visit 10 (Phase I)

Study team members visit the participant the following morning to remove PSG.

Above procedures take about 30min 'active' engagement to complete.

6.2.11 Visit 11 (Phase I)

Participant has a fasted blood draw conducted by qualified Clinical Research Center (CRC; Noll Laboratory) staff. This visit (11) may be combined with the previous visit (10) if a participant elects for the blood draw to occur in their personal residence.

- -Participant returns the bedside controller.
- -Participants keep the bed pad portion of the sleep pad system for re-use later in the study.

Above procedures take about 30min 'active' engagement to complete.

6.2.12 Washout and Visit 12

The ~5th study week will consist of a "washout" during which no participants use the functional features of sleep pad system. However, throughout this week, participants do continue 24hr actigraphy monitoring, continue to complete daily sleep diary and device usage survey entries (~2min combined), and continue to complete the weekly REDCap survey all noted in the general summary above.

Note that an optional pause of study activities at the conclusion of the Washout week will be available. Participants are not required to continue passive (actigraphy) monitoring or surveys during any pause period (>1wk). Maximum duration of appropriate pause will be determined by Co-Investigators, but is not anticipated to exceed 10wks.

Total anticipated Washout active study time commitment is 30min.

At the beginning of study week 6, a participant receives again for use the bedside controller, either by delivery (in-person or by mail) or pickup from PSU-UP campus. Because receipt may occur in person, this is considered the "12th visit" although not necessarily requiring a "visit".

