2.0 Background

2.1 Study Rationale

Studying the relationship between sleep and health is important to understand how we might optimize sleep to the benefit of our overall mental and physical well-being.

Normal healthy sleep is generally categorized as the absence of sleep disturbances and disorders, but it also involves obtaining sufficient duration, good quality, and appropriate timing. Insufficient or poor sleep results in a greater risk for adverse health outcomes and complication, and also has been associated with increased mortality rates and diminished quality of life. Therefore, sleep is associated with overall well-being and is necessary for health maintenance. This pilot intervention is expected to provide evidence for the feasibility and efficacy of a sleep-enhancing intervention that generates and systematically applies magnetic field potentials to a sleeper's environment. The exact mechanism of this intervention is not yet understood.

Insufficient sleep, as well as the negative affect and perceived stress that tend to co-occur with poor sleep, have all been linked with higher levels of peripheral inflammation^{12,13}. A preponderance of work investigating links between sleep and inflammation is focused on adverse effects of sleep *disruption*; here, we hope to focus on whether changes can be effected by sleep *improvement*, and specifically by sleep improvement via this unique intervention type (non-invasive, unobtrusive electromagnetic field potential).

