6.2.17 Visit 17 (Phase 2)

Participant has a fasted blood draw conducted by qualified Clinical Research Center (CRC; Noll Laboratory) staff. This visit (17) may be combined with the previous visit (16) if a participant elects for the blood draw to occur in their personal residence.

Upon completion, participants receive a ~1min survey to assess both their awareness of their assigned condition order and so that they have the opportunity to request to be contacted with information about their randomized order after the study concludes (please refer to CATS attachment, "End of Study Survey"). Participants also receive an optional ~1min survey via email that is administered through REDCap shortly after ending participation (please refer to CATS attachment, "Follow-Up Survey").

Above procedures take about 30min 'active' engagement to complete.

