8.0 Risks

PSG and ambulatory (actigraphy) monitoring devices are typical clinical outpatient procedures that pose mild risks that include but are not limited to: the attachment and removal of monitoring electrodes may cause mild, temporary discomfort; participants may have difficulty sleeping while the monitoring equipment is attached; participants may experience mild frustration maneuvering around equipped devices; location where sensors are worn or applied may experience temporary skin irritation. It is possible that wearing monitoring equipment may be bothersome enough to interfere with sleep quality (although that is not an intended purpose of any monitor/intervention in this research), which could make subjects feel irritable or more tired during the day time.

To minimize these risks, we thoroughly clean devices between subjects, spread out overnights involving PSG, and can adjust the application site of some sensors as-needed based on reported subject comfort/reactivity.

Participants may feel uncomfortable answering some survey questions. Participants may elect to not answer any survey question that they do not want to, but not answering may affect their study eligibility to initiate or continue in the study, or to be included in research data analyses.

Blood draws often cause mild pain, swelling or bleeding. Fasting before blood draws may be uncomfortable. There may be some bruising (blood under the surface of the skin), which can be minimized by pressing on the site after the needle is removed. There is also a small chance of infection, dizziness, or fainting. These risks will be minimized, and most likely eliminated, by having trained CRC staff perform the blood draw on a seated or reclined participant using sterile supplies. If dizziness or fainting occurs, the symptoms will be alleviated by closely monitoring the participant, directing them to lie flat with their feet raised, and by offering a snack and/or beverage. Participants demonstrating these symptoms may be asked to stay at the blood draw location (i.e. PSU CRC) or to permit study staff to stay at the blood draw location (i.e. in their personal residence) until staff have confirmed that the participant is well enough.

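### Nothing keeps a participant's two phase blood draws on the same footing relative to the last PSG night, which adds avoidable noise to the active-sham biomarker difference

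*Combined protocol and SAP*

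**What the plan says.** Blood is drawn three times: at Visit 5 (Baseline), Visit 11 (Phase 1) and Visit 17 (Phase 2).

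- **Phase 1 (6.2.11):** the draw "may be combined with the previous visit (10) if a participant elects for the blood draw to occur in their personal residence".
- **Phase 2 (6.2.17):** the draw "may be combined with the previous visit (16) if a participant elects for the blood draw to occur in their personal residence".
- **Visits 10 and 16 (6.2.10, 6.2.16):** each is the morning after an overnight recording: "Study team members visit the participant the following morning to remove PSG".
- **Baseline (6.2.5):** "Participant has a fasted (~8hrs immediately preceding the appointment, no food and limited water intake) blood draw". No option to combine with Visit 4 is given, and no interval after Visit 4 is stated.
- **Who can choose:** under 6.2, participants living more than about 20 minutes from campus must attend campus, so the home option is not open to them.
- **PSG and sleep (8.0):** it is possible that "wearing monitoring equipment may be bothersome enough to interfere with sleep quality".
- **Sleep and inflammation (2.1):** insufficient sleep, and the negative affect and stress that accompany it, "have all been linked with higher levels of peripheral inflammation".
- **Use of the samples:** inflammatory biomarkers are a secondary endpoint (1.3). Section 7.3 compares conditions within participants on change from Baseline and mentions no record of, or adjustment for, draw timing.

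**The concern.** A combined draw follows a PSG night by construction. A separate draw has no fixed day or hour, so it may follow an ordinary night. The option is written once for each phase with nothing linking the two, so one person can have a combined draw in one phase and a separate draw in the other. The protocol itself treats PSG as a possible disturbance of sleep, and poor sleep as a correlate of inflammation. The night before the draw is therefore a plausible source of variation in the biomarker that has nothing to do with the pad.

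At stake is the precision of the biomarker effect sizes. The study aims to complete 10 participants (7.1), and its purpose is to supply effect sizes for future studies (1.1, 7.2). Avoidable within-person noise carries directly into those estimates. If draw timing goes unrecorded, it cannot be reliably recovered later.

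**Working it through.** The plan gives no figure on this point, so there is nothing to reproduce. The check has three steps.

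**1. Does the shared Baseline remove the problem?** Let A, S and B be a participant's biomarker values under active, under sham and at Baseline. The contrast of change scores is (A − B) − (S − B) = A − S. Baseline cancels. It can neither cause nor correct a mismatch between the two phase draws.

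**2. How many participants could be mismatched?** Let p be the chance that a participant takes the combined draw in a given phase. The documents give no value, so p is an assumption. If the two choices are independent, P(choices differ) = 2p(1 − p). With n = 10 completers (7.1), all assumed eligible for home visits:

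| p | 2p(1 − p) | Expected of 10 | P(at least one) = 1 − [1 − 2p(1 − p)]^10 |
|---|---|---|---|
| 0.1 | 0.18 | 1.8 | 86% |
| 0.3 | 0.42 | 4.2 | 99.6% |
| 0.5 | 0.50 | 5.0 | 99.9% |

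Under independence, p = 0.5 gives the largest value. If every participant repeats the Phase 1 choice, the number is 0. Participants with no home option lower it too: if 3 of the 10 lived too far away, the p = 0.5 figure would be 7 × 0.50 = 3.5.

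These are counts of differing choices. A differing choice means a differing night only if the separate draw falls on a later day than PSG removal. Conversely, two separate draws can differ from each other, because no interval is stated.

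**3. What does a mismatch do to the active-sham difference?** Let δ be the unknown effect of a PSG night on the biomarker, and take separate draws to follow PSG-free nights. Each participant's A − S then contains δ × D. Here D is +1 if only the active draw followed a PSG night, −1 if only the sham draw did, and 0 otherwise. If the choice is unrelated to condition, D has mean 0 and variance 2p(1 − p). The mean over 10 participants is shifted by a chance amount with SD = δ × √[2p(1 − p)/10]:

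- p = 0.1: √(0.18/10) = 0.13 δ
- p = 0.3: √(0.42/10) = 0.20 δ
- p = 0.5: √(0.50/10) = 0.22 δ

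The expected shift is zero. The cost is added variance and chance imbalance.

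**The case against.** The strongest case against is that the mismatch is only possible and its consequence has not been shown to be material.

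- **Choices may persist.** Preference for home or campus probably depends on distance and convenience, which change little over 8 weeks. This stands, and it is why the range starts at 0. The protocol does not, however, require persistence.
- **A separate draw could still fall on the PSG-removal morning**, and the fasting requirement makes a morning draw likely. Both stand, but neither the day nor the hour is fixed.
- **The mechanism is general.** Section 2.1 does not say that one disturbed night moves a biomarker, and 8.0 says only that PSG may interfere with sleep. This stands: δ is unknown and could be small.
- **Sleep before each phase draw is measured anyway**, by round-the-clock actigraphy and twice-daily diaries (6.2). This helps in part, but no analysis using these data is planned for the biomarkers.

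A reader might go further and infer that the active-sham comparison is confounded, so that an apparent device effect could be a systematic PSG effect. The documents do not support that. Order is randomised (6.4.3) and double-blind (6.4.5), so while the blind holds the choice of draw should be largely unrelated to condition. A reader might also infer that every participant has this choice in each phase. The campus-attendance rule in 6.2 excludes those living too far away.

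**Conclusion.** The point holds as a matter of standardisation and precision. For participants eligible for home visits, the protocol allows the two compared samples to follow different kinds of night and sets nothing to prevent it. The number with differing choices runs from 0 to about 5 of 10 completers. The upper figure assumes independent, evenly split choices and that all 10 are eligible for home visits. The resulting chance shift in the mean active-sham difference has an SD of 0.13 to 0.22 times the PSG-night effect for p from 0.1 to 0.5, and falls to 0 if choices and intervals are kept the same. The PSG-night effect itself is not in the documents, so the shift cannot be put in biomarker units. One secondary endpoint of a pilot is affected. The change is worth making because it is cheap and has to be made before samples are drawn.

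**What to change.** **Amend 6.2.11 and 6.2.17** so that each participant's draw setting, interval after the last PSG night and clock window are the same in Phase 1 and Phase 2.

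**Record clock time and hours since PSG removal** at all three draws, and add to 7.3 a sensitivity analysis of the biomarkers that uses them. If fixed timing proves impractical, the two recorded fields alone would still permit that analysis.

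**Match Visit 5 to the same interval after Visit 4 only where this needs no new Baseline home draw.** Section 6.2.5 offers no home option. Visit 4 is also where compliance and PSG success decide who continues (6.2.4), so a draw there could take blood from people who then do not proceed. Because Baseline cancels in the active-sham contrast, this part is optional.

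While setting the interval, the device-return steps should also be reconciled. In Phase 1 the controller is returned at the draw visit (6.2.11), but in Phase 2 the system is returned at Visit 16 (6.2.16), before the draw visit. Equal intervals after PSG would therefore not by themselves give equal intervals after the last device night. This is a related matter on which the verdict does not rely.

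**Cost:** scheduling wording and two recorded fields, with no added draw or visit. Participants lose the freedom to switch draw setting between phases.
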